22.1. Tipping point analysis and Multiple imputation (MI) methods

Prior to conducting tipping point analysis and MI imputation, subjects with data after the receipt of rescue therapy will be considered treatment failure i.e., non-responder for analysis. Tipping point analysis and MI imputation will be performed for subjects with real missing data which is not induced by the receipt of rescue therapy.

Tipping point analysis will be performed by converting non-responders due to missing data to responders in successive increments (Δ) for both treatment groups to assess the robustness of analysis. The value of Δ that overturns (i.e. non-significant) the primary results will represent the tipping point. A graphic display of all possible combination of the number of responders among both treatment groups will be presented.

Multiple imputation (MI) methods for missing data. The MI imputation will be carried out as follows.

1. Imputation Phase
 - a. A 50 imputed datasets with a monotone missing pattern will be created using SAS MI procedure based on the observed data (Markov-Chain-Monte-Carlo method, MCMC). The seed to be used is 118161 (the Protocol number). Pattern of missing data will be evaluated and it is expected that the pattern of missing data will be monotonic. For non-monotone missing data patterns, MCMC method of MI procedure will be used to impute enough data so that the remaining missing data is monotone.
 - b. Each of the imputed datasets will be used to generate 50 complete datasets, using following approaches:
 - i. Ordinal data (e.g., IGA score): A logistic regression method to impute the ordinal missing data, including treatment, randomization strata, and assessments from earlier time points as covariates. Potential auxiliary variables (e.g., the number of injections) may be explored and added into the imputation model. Response or total score of the subjects will be derived using these imputed data.
 - ii. Continuous data (e.g., EASI score): A linear regression model including treatment, randomization strata, and assessments from earlier time points as covariates will be used to impute the score. Potential auxiliary variables (e.g., the number of injections) may be explored and added into the imputation model. Response or total score of the subjects will be derived using these imputed data.
2. Analysis Phase: The analysis will be conducted using the complete datasets.
 - a. Binary endpoint: The complete datasets will be modelled for the endpoint using CMH method. Proportion of responders in each treatment arm, difference and standard error will be calculated.
 - b. Continuous endpoint: The complete datasets will be analyzed using ANCOVA including treatment group and randomization stratification factors as factors and appropriate Baseline values as a covariate, if applicable. LSM means in each treatment arm, difference and standard errors will be calculated.
3. Pooling Phase: The results from the analysis phase will be combined as follows.
 - a. Binary endpoint: The results from the CMH analysis of the multiple imputed datasets will be combined using the Rubin (1987) and Li et al (1991) approach to produce pooled CMH statistics

This document is confidential.

and p-value. Proportion of responders in each treatment arm, difference and standard error will be combined using the MIANALYZE procedure in SAS.

- b. Continuous endpoint: The LSMeans in each treatment arm, difference and standard errors from the ANCOVA of the multiple imputed datasets will be combined using the MIANALYZE procedure in SAS.

22.2. Example SAS Code

1. The example SAS code for CMH model is listed as below:

```
Proc freq data=analysis_data;  
  
    Tables stratum*trt*resp/ cmh alpha=0.1;  
Run;
```

2. The example SAS code for MMRM model is listed as below:

```
Proc mixed data = analysis_data;  
  
    class stratum trtp avisit subjid;  
    model chg = base stratum trtp avisit trtp*avisit base*avisit / ddfm=kr;  
    repeated avisit / subject=subjid(trtp) type=un;  
    lsmeans trtp/ cl diff;  
    lsmeans trtp*avisit/ slice=avisit cl diff;  
run;
```

3. The example SAS code for ANCOVA model is listed as below:

```
Proc mixed data = analysis_data;  
    class stratum trtp;  
    model chg = base stratum trtp;  
    lsmeans trtp/ cl diff;  
run;
```

The example SAS code for imputation phase by PROC MI:

```
proc mi data=analysis_data seed=118161 minimum=0 maximum=xx nimpute=50 out=out_data;  
    mcmc impute=monotone nbiter=200 niter=100;  
    var base stratum y4 y8 y12 y16;  
run;
```

```
Proc mi data = analysis_data seed=118161 minimum=0 maximum=xx nimpute=number_of_imputations  
out=out_data;  
    class trtp stratum;  
    monotone reg (/details);  
    var base stratum y4 y8 y12 y16;  
run;
```

This document is confidential.

Statistical Analysis Plan for Interventional Studies

Sponsor: Galderma Research & Development, LLC; Protocol No.: RD.06.SPR.118161

For IGA,

```
Proc mi data = analysis_data seed=118161 minimum=0 maximum=xx nimpute=number_of_imputations
out=out_data;
  class trtp stratum;
  monotone logistic (/details);
  var base stratum y4 y8 y12 y16;
run;
```

1.0

CD14152.SPR118161.SAP.V01

Approved 10-Nov-2022 00:00:00

This document is confidential.

5. The example SAS code for pooling phase for ANCOVA model by PROC MIANALYZE:

```
proc sort data=diff; by avisitn trtp; run;  
proc sort data=lsn; by avisitn trtp; run;  
proc mianalyze data=diff; by avisitn trtp;  
modeffects estimate;  
stderr stderr;  
ods output ParameterEstimates=estdiff; run;
```

```
proc mianalyze data=lsn; by avisitn trtp;  
modeffects estimate;  
stderr stderr;  
ods output ParameterEstimates=estlsn; run;
```

1.0

CD14152.SPR118161.SAP.V01

Approved 10-Nov-2022 00:00:00

This document is confidential.

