be performed per investigator's judgement.. Subjects requiring rescue therapy between scheduled visits should return to the clinic for an unscheduled visit for investigator assessments of efficacy before starting rescue therapy.

^e CCI

^d Subjects discontinued prematurely should complete ET assessments according to: Visit 6/Week 16 if during the initial treatment period **or** Visit 14/Week 48 if during the maintenance period **and** a final/follow-up visit 12 weeks after the last study drug injection (for subjects not participating in the LTE study). Subjects who require rescue therapy (with or without study medication discontinuation) must continue with study visits until: Visit 6/Week 16 if during the initial treatment period **or** until Visit 10/Week 32 if during the maintenance period to be considered for LTE eligibility. (If during the maintenance period, rescue is needed after the Week 32 visit, no wait period is required.) See Section 8.5.1 for details.

^e The follow-up visit will be conducted for subjects who decline or are not eligible to enter the LTE study and should be conducted 12 weeks after the last study drug injection. (The follow-up visit is not required for subjects who will rollover to the LTE study.)

^f The run-in period begins at least 2 weeks (ie, 14 days) before Day 1/baseline. Subjects receiving rescue therapies during the run-in period are not eligible to participate in the study.

^g Patient-reported outcome assessments and designated safety measurements should occur before investigator assessments, laboratory sample collections, and study drug administration.

^h CCI

^k Assessments to be completed by subjects for 7 consecutive days before the designated target visit dates during study treatment.

^l Optional subject interviews will be conducted at the end of the initial treatment period between Week 16 and Week 18. See Section 9.7.15 for details.

^m Optional photographs of AD lesions will be performed only for consenting subjects at selected sites. See Section 9.8 for details.

ⁿ Subjects with a history of asthma will complete the ACT (and PEF testing) at each scheduled visit. Subjects with de novo asthma will complete the ACT (and PEF testing) beginning from de novo diagnosis and at all subsequent scheduled visits. See Section 9.2.9.1 for details.

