8.4. Analysis Visit Windows

Efficacy by-visit summaries will use the analysis visit. Unscheduled and early termination visits will be windowed based on the following analysis visit window which is based on study day. If multiple measurements are taken within the same window, the one taken closest to the target study day will be used for the analysis. If there are multiple measurements with same difference from target day, the later assessment should be used for the analysis.

Table 8-1: Analysis Visit Window

Analysis Visit	Target Study Day	Visit Window for EASI, IGA, BSA, SCORAD, Rescue therapy	Visit Window for PGIS-P, PGIS-SD, PGIC-P, PGIC-SD	Visit Window for DLQI/cDLQI, HADS, EQ-5D, POEM, WPAI:AD, Pain intensity/frequency, PGAD, PGAT, PIQs*
Baseline	1	<=1	<=1	<=1
Week 4	29	2 to 42	NA	NA
Week 8	57	43 to 70	2 to 81	2 to 84
Week 12	85	71 to 98	NA	NA
Week 15	106	NA	82 to 108	NA
Week 16	113	99 to 126	>=109	85 to 168 except for PIQs; >=85 for PIQs
Week 20	141	127 to 154	NA	NA
Week 24	169	155 to 182	NA	NA
Week 28	197	183 to 210	NA	NA
Week 32	225	211 to 238	NA	169 to 280 except for PIQs
Week 36	253	239 to 266	NA	NA
Week 40	281	267 to 294	NA	NA
Week 44	309	295 to 322	NA	NA

This document is confidential.

Statistical Analysis Plan for Interventional Studies

Sponsor: Galderma Research & Development, LLC; Protocol No.: RD.06.SPR.118161

Week 48	337	>=323	NA	>=281 except for PIQs
---------	-----	-------	----	-----------------------

* PIQs assessment is available during Initial period only. Visit window after Week 16 will not be applicable for PIQs.

Analysis visit of diary (ePRO) data will be defined depending on the data collection as below.

For the diary data at post-baseline visit, only the diary data assessed within the timeframe below (+1 hour to end time in spec) will be considered for analysis. If >1 diary recorded on a day (within window), only one of them to take for analysis (i.e. latest one for evening diary, earliest one for morning diary).

- Evening assessment (PP/AP NRS, Topical medication, PCS) recorded from 17:00:00 to 00:59:59
- Morning assessment (SD NRS, morning sleep diary) recorded from 5:00:00 to 17:59:59

Consecutive daily assessment:

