10.1.2. Sensitivity Analyses of Primary Efficacy Endpoint

The following sensitivity analyses for both populations will be conducted for the robustness of the primary analyses.

- Same analysis on PP population
- Tipping point analysis (see Appendix 22.1)
- Multiple imputation (MI) methods (see Appendix 22.1)
- Last Observation Carried Forward (LOCF) imputation method for missing data. Missing post-baseline values will be carried forward from the last non-missing post-baseline value. Baseline value will not be carried forward to post-baseline value.
- Observed Case (OC) - no data will be imputed. For this analysis, if any rescue medication is received, data post-rescue therapy will be analyzed as observed (i.e., not considered treatment failure).
- Same analysis on ITT using 'actual stratum' instead of 'stratum at the randomization'.

Tipping point analysis, multiple imputation methods, LOCF and OC analysis will be performed on the ITT population. Except OC analyses, assessments on or after rescue therapy used will be considered as treatment failure and will be considered as non-responders for analysis.

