AP NRS will determined by an average as described above at every week from Baseline to Week 16 as a continuous variable of the Initial Period. Descriptive summary of AP NRS will be provided for ITT population. Absolute change and percent change from Baseline for the AP NRS score will also be included in the summary.

Change from Baseline in PP NRS at each analysis visit up to Week 16 will be analyzed using ANCOVA, with missing values imputed using MI under MAR assumption, and MMRM. For the MI and MMRM analyses the least squares means (LSMeans), standard error of LSMean, and 95% CI for change from Baseline, as well as the difference in LSMean between the treatment groups, the two-sided 95% CI, and associated p-value will be presented. In addition, percent change from Baseline in PP NRS at each analysis visit up to Week 16 will be analyzed using MMRM.

Change from Baseline in percentage of itch-free days based on PP/AP NRS (score of 0 or 1) will also be summarized descriptively by visit.

This document is confidential.

Improvement in PP/AP NRS will be calculated using Baseline as the reference point for change in PP/AP NRS score. The proportion of subjects with PP NRS improvement ≥ 4 will be presented using OC, non-responder and LOCF. The proportion of subjects with an improvement of PP NRS ≥ 4 at Week 8 and Week 12, the proportion of subjects with a PP NRS < 2 at Week 1, Week 2, Week 8 and Week 12, the proportion of subjects with AP NRS ≥ 4 at each visit up to Week 16, and the proportion of subjects with AP NRS < 2 at each analysis visit up to Week 16 will be analyzed using non-responder imputation. The estimate of treatment unadjusted and strata-adjusted differences with the corresponding 2-sided 95% confidence intervals, and p-values from the Cochran-Mantel-Haenszel test will be presented.

Line plot for proportion of subjects with PP NRS improvement ≥ 4 and for proportion of subjects with PP NRS < 2 using Non-responder imputation will be presented for Initial Period on the ITT population.

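### The PROC MI examples in SAP 22.2 omit treatment from the imputation model that SAP 22.1 and Protocol 10.1.11 require; if copied, they would usually shrink the MI treatment difference

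*SAP*

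**What the plan says.** The governing text is SAP 22.1, step 1b, which carries over Protocol 10.1.11. For continuous scores such as EASI it reads "A linear regression model including treatment, randomization strata, and assessments from earlier time points as covariates will be used to impute the score". For IGA it reads "A logistic regression method to impute the ordinal missing data, including treatment, randomization strata, and assessments from earlier time points as covariates". Step 1a, the MCMC step that makes the missing pattern monotone, names no covariates.

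SAP 22.2 then gives three PROC MI examples: MCMC, monotone regression, and monotone logistic for IGA. All three share the list "var base stratum y4 y8 y12 y16". In the two monotone calls treatment occurs only in "class trtp stratum"; the MCMC call has no CLASS statement. No call has a BY statement for treatment. Neither MONOTONE statement writes out a model, so the predictors are whatever precedes each score in VAR.

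MI has two uses in the plan. It is a sensitivity analysis for the co-primary and key secondary endpoints (SAP 10.1.2 and 10.2). It also feeds the ANCOVA of continuous endpoints; change in PP NRS, for example, "will be analyzed using ANCOVA, with missing values imputed using MI under MAR assumption, and MMRM" (SAP 10.3.3). The main analysis of the co-primary and key secondary endpoints counts missing values as non-response (SAP 10.1.1 and 10.2).

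**The concern.** Text and code specify different imputation models. An imputation model without treatment fits one regression to both arms. A subject with no Week 16 score then gets a value that depends on stratum and earlier scores but not on arm. Whatever part of the drug effect those scores do not already show is lost for that subject, so the MI difference is usually pulled toward zero.

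The slip would be easy to miss, because leaving treatment out gives a plausible result rather than an obvious failure. What is at stake is the MI check on the co-primary non-responder results and the MI-based ANCOVA of EASI, BSA and SCORAD.

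**Working it through.** **1. Text against code**

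| Step | SAP 22.1 asks for | SAP 22.2 supplies |
|---|---|---|
| 1a, MCMC | no covariates named | baseline, stratum, visit scores; no treatment |
| 1b, continuous | treatment, strata, earlier scores | baseline, stratum, earlier scores; treatment in CLASS only |
| 1b, IGA | the same, by logistic regression | the same omission; visit scores not in CLASS |

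Two of the three calls contradict explicit text. The MCMC call is a fault of the template only. The IGA call has a second gap: the logistic method imputes classification variables, and `y4` to `y16` are not declared as such.

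**2. Which endpoints the template fits.** Weeks 4, 8, 12 and 16 are the initial-period visits for EASI, IGA, BSA and SCORAD (SAP Table 8-1). PP NRS and SD NRS are weekly averages (Table 8-2). Quality-of-life scales are taken at baseline, Week 8 and Week 16. The two composite key secondary endpoints combine diary data with EASI or IGA.

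**3. Extreme bound.** Take the plan's 15% dropout, 2:1 allocation and assumed rates, and suppose that earlier visits carry no information. Missing responses are then imputed at the pooled rate in both arms.
- EASI-75: pooled (2×49 + 19)/3 = 39%. Arms: 0.85×49 + 0.15×39 = 47.5% and 0.85×19 + 0.15×39 = 22.0%. The difference is 25.5 points instead of 30.
- IGA success: pooled (2×30 + 12)/3 = 24%. Arms: 29.1% and 13.8%. The difference is 15.3 points instead of 18.

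Both lose 15%, the missing fraction itself.

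**4. Hand check with one earlier score.** Assume unit variance, within-arm correlation ρ, and the same effect δ at Weeks 12 and 16. The slope with arms pooled is b = (ρ + (2/9)δ²)/(1 + (2/9)δ²), and the loss is m(1 − b) for missing fraction m. With δ = 0.5, (2/9)δ² = 0.0556. With m = 0.15:
- ρ = 0.5: b = 0.526, loss 7.1%
- ρ = 0.7: b = 0.716, loss 4.3%
- ρ = 0.85: b = 0.858, loss 2.1%

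**5. Simulation on the EASI/IGA schedule.** Each scenario had 300,000 subjects, 2:1, with a 0.5 SD effect at Week 16. The effect was either full from the first visit or built up. Correlations were 0.5 to 0.85, and dropout was equal by arm and uniform over Days 2–112. Scores were imputed visit by visit with and without treatment, followed by ANCOVA at Week 16. Loss = 1 − (estimate without)/(estimate with). Early termination data were placed as SAP 8.4 directs ("Unscheduled and early termination visits will be windowed based on the following analysis visit window which is based on study day"), since Protocol 8.1.2 note d says "Subjects discontinued prematurely should complete ET assessments according to: Visit 6/Week 16 if during the initial treatment period".

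| Scenario | Loss |
|---|---|
| 15% dropout, all attend early termination (13.1% lack Week 16) | 3.1–10.8% |
| 15%, half attend | 4.6–11.8% |
| 15%, none attend | 6.2–12.8% |
| 15% miss Week 16 only | 1.7–10.1% |
| 5% dropout, all attend | 1.0–3.6% |
| 15%, all attend, earlier effect 1.5 times the Week 16 effect | 0.5% gain to 6.6% loss |
| 15% miss Week 16 only, earlier effect 1.5 times the Week 16 effect | 2.8% gain to 2.9% loss |

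Repeating the first scenario with separate code gave 2.5–11.1%. A trial-size run (1,000 trials of 500:250, 10 proper imputations, correlation 0.7) gave 0.499 with treatment and 0.457 without, a loss of about 8%.

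In binary terms, using a normal latent score at the plan's rates with 15% dropout and all attending, the MI difference falls by 0.7–3.2 points for EASI-75 and 0.5–1.9 points for IGA success.

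**The case against.** The strongest reply is that this is only an example. It contains placeholders for the maximum and the number of imputations. Its monotone calls read the analysis dataset rather than the MCMC output, so a programmer must rewrite it anyway. SAP 10.1.2 points to 22.1, where the text is correct, and treatment in CLASS shows what was intended. All of that is true, and it means there is no proof that any result will be biased. It does not remove the mismatch. This is the only imputation code in an approved SAP, it carries the study seed, 50 imputations and the study's visit weeks, and the MMRM and ANCOVA examples beside it do include treatment.

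Two further points stand in full. First, a reader might infer that every MI analysis is exposed, including PP NRS, SD NRS, DLQI and similar scales. The documents do not support that: the template's visits do not match theirs, so they are affected only if their own code repeats the omission. Protocol 10.1.10 and SAP 8.3 also allow LOCF for quality-of-life scales. Second, the sizing rests on correlations, effect timing and attendance that the documents do not give. It also ignores rescue: SAP 22.1 treats post-rescue data as failure and imputes only data missing for other reasons, so the imputed fraction may be smaller than assumed.

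**Conclusion.** The two monotone examples are wrong as written against SAP 22.1 and Protocol 10.1.11, and the MCMC example should be corrected with them. If copied, they would usually attenuate the MI difference by roughly 3 to 11% for EASI-type measures at 15% dropout with early termination visits attended. Less missing data shrinks this. An effect that wanes by Week 16 could instead give a small inflation, up to about 3%.

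The direct reach is the MI sensitivity analysis of the co-primary endpoints and the MI-based ANCOVA of EASI, BSA and SCORAD. Those three change scores also have MMRM tables, and the co-primaries also have tipping-point, LOCF, observed-case and per-protocol checks.

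Two stronger readings should be set aside. One is that the main efficacy conclusions are at risk; they are not, because those tests use non-responder imputation. The other is that the arms are fully pooled, with a 15% loss. That would need every dropout to have no post-baseline information, whereas early termination visits are windowed by study day and subjects who stop drug are asked to keep attending (Protocol 8.5.1).

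Severity: a minor appendix-code correction.

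**What to change.** In SAP 22.2, before programming:

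- **Both monotone calls:** put treatment in VAR ahead of the visit scores, for example `var trtp stratum base y4 y8 y12 y16`.
- **IGA call:** also list `y4 y8 y12 y16` in CLASS (and `base`, if treated as categorical). Adding treatment alone would not make this call match the ordinal logistic model in 22.1.
- **MCMC call:** run it BY treatment, or add a numeric treatment indicator to VAR.
- **Chaining:** have the monotone step read the MCMC output BY `_IMPUTATION_` with `NIMPUTE=1`, giving 50 completed datasets.
- **Other endpoints:** state that diary and quality-of-life measures use the same model, treatment included, with their own visit variables.

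The cost is a few lines of appendix code and one sentence of text. No new data are needed and no main test changes.

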22.3. Potentially clinically significant ranges – Adults

1.0

CD14152.SPR118161.SAP.V01

Approved 10-Nov-2022 00:00:00

Test Parameter	Reference range (as per Lab Manual)		Potentially Clinically Significant Ranges (min and/or max limits)	SI Units
	LLN	ULN		
SERUM				
White Blood Cell Count (WBC)	4.00	10.70	<3.0 at post-baseline and ≥3.0 at baseline >15.0 at post-baseline and ≤15 at baseline	x10E9/L
Neutrophils (absolute)	1.60	7.40	<1.5 at post-baseline and ≥1.5 at baseline >9 at post-baseline and ≤9 at baseline	x10E9/L
Eosinophils (absolute)	0.00	0.70	>0.7 at post-baseline and ≤0.7 at baseline	x10E9/L
Basophils (absolute)	0.00	0.20	>0.2 at post-baseline and ≤0.2 at baseline	x10E9/L
Monocytes (absolute)	0.10	0.90	>0.9 at post-baseline and ≤0.9 at baseline	x10E9/L
Lymphocytes (absolute)	1.00	4.00	<0.8 at post-baseline and ≥ 0.8 at baseline >4.0 at post-baseline and ≤ 4.0 at baseline	x10E9/L
Hemoglobin *Male **Female	* 135.00 ** 120.00	* 175.00 ** 160.00	* <100 g/L at post-baseline and ≥ 100 g/L at baseline * ≥200 g/L at post-baseline and < 200 g/L at baseline ** <90 g/L at post-baseline and ≥ 90 g/L at baseline ** ≥180 g/L at post-baseline and < 180 g/L at baseline	g/L
Hematocrit *Male **Female	* 0.40 ** 0.36	* 0.52 ** 0.46	<0.30 at post-baseline and ≥ 0.30 at baseline >0.6 at post-baseline and ≤ 0.6 at baseline	L/L
Platelets	150.00	350.00	<100 at post-baseline and ≥ 100 at baseline >700 at post-baseline and ≤ 700 at baseline	x10E9/L
Sodium	135.00	148.00	<129 at post-baseline and ≥ 129 at baseline >150 at post-baseline and ≤ 150 at baseline	mmol/L
Potassium	3.50	5.30	<3.5 at post-baseline and ≥ 3.5 at baseline >5.5 at post-baseline and ≤ 5.5 at baseline	mmol/L
Calcium - total	2.14	2.62	<2 at post-baseline and ≥ 2 at baseline	mmol/L
Chloride	98.00	110.00	<95 at post-baseline and ≥ 95 at baseline >115 at post-baseline and ≤ 115 at baseline	mmol/L
Glucose	3.90	6.90	<3 at post-baseline and ≥ 3 at baseline >13.9 at post-baseline and ≤ 13.9 at baseline	mmol/L
Creatinine *Male **Female	* 62 ** 44	* 106 ** 80	>1.5 x ULN at post-baseline and ≤1.5 x ULN at baseline	µmol/L
Blood urea nitrogen (BUN)	2.1	8.9	>8.9 at post-baseline and ≤8.9 at baseline	mmol/L
AST	0.00	41.00	>3 x ULN at post-baseline and ≤3 x ULN at baseline	U/L
ALT	0.00	45.00	>3 x ULN at post-baseline and ≤3 x ULN at baseline	U/L
Alkaline phosphatase *Male **Female	* 40 ** 35	* 129 ** 104	>2.5 x ULN at post-baseline and ≤2.5 x ULN at baseline	U/L
Bilirubin total	0.00	21.00	>1.5 x ULN at post-baseline and ≤1.5 x ULN at baseline	µmol/L

This document is confidential.

1.0

CD14152.SPR118161.SAP.V01

CPK				
*Male	20.00	* 200	>2.5 x ULN at post-baseline and ≤2.5 x ULN at baseline	U/L
**Female		** 180	>2.5 x ULN at post-baseline and ≤2.5 x ULN at baseline	
GGT	0.00	65.00	>2.5 x ULN at post-baseline and ≤2.5 x ULN at baseline	U/L
Protein total	60.00	85.00	<50 at post-baseline and ≥50 at baseline >95 at post-baseline and ≤95 at baseline	g/L
Albumin	32.00	55.00	<30 at post-baseline and ≥30 at baseline	g/L
Uric acid	* 0.24	* 0.51	* >0.51 at post-baseline and ≤0.51 at baseline	mmol/L
*Male				
**Female	** 0.15	** 0.45	** >0.45 at post-baseline and ≤0.45 at baseline	
Cholesterol total	0.00	5.17	>7.75 at post-baseline and ≤7.75 at baseline	mmol/L
Triglycerides	0.00	2.25	>3.42 at post-baseline and ≤3.42 at baseline	mmol/L
VITAL SIGNS and WEIGHT				
Pulse rate	N/A	N/A	≤50 bpm and decrease from baseline ≥20 bpm ≥120 bpm and increase from baseline ≥20 bpm	beats/min
Diastolic blood pressure	N/A	N/A	≤45 mmHg and decrease from baseline ≥10 mmHg ≥110 mmHg and increase from baseline ≥10 mmHg	mmHg
Systolic blood pressure	N/A	N/A	≤95 mmHg and decrease from baseline ≥20 mmHg ≥160 mmHg and increase from baseline ≥20 mmHg	mmHg
Weight	N/A	N/A	≥5% increase from baseline ≥5% decrease from baseline	

